6.4. Measures to Minimize Bias: Randomization and Blinding

6.4.1. Randomization and Stratification

Main study: All subjects will be centrally randomized 16:8:6:24:15 to Placebo QW, Placebo Q2W, pegozafermin 15 mg QW, 30 mg QW and 44 mg Q2W, respectively. The randomization will be stratified by T2DM status (yes vs. no) and fibrosis stage (F2 vs. F3). For the purposes of stratification, subjects will be considered to be T2DM status positive if any of the following

criteria are met: current medical history of T2DM, current use of anti-glycemic medication(s) for T2DM, or screening laboratory values of $\geq 6.5\%$ for HbA1c or ≥ 126 mg/dL for fasting plasma glucose. The proportion of subjects enrolled with MRI-PDFF $<8\%$ may be limited at the Sponsor's discretion.

In the Extension study, subjects randomized to placebo QW in the Main study will be re-randomized 1:1 to pegozafermin 30 mg QW (n=21) or placebo (n=21).

All subjects will be centrally assigned to randomized IP using an Interactive Response Technology (IRT).

6.4.2. Assignment of Subject Number and Investigational Product

At the Screening visit, each subject will have a unique subject number assigned for subject identification in the study. Subjects who are rescreened will retain the original identification number; a new ID will not be assigned.

IP will be dispensed at the study visits as summarized in the SoA. The IP kit number(s) will be assigned by the IRT system upon obtaining the subject's randomized treatment group.

For subsequent visits when IP is dispensed, the IRT system will assign IP kits based on the subject's randomized treatment group in the Main study and the Extension study accordingly.

6.4.3. Blinding

Subjects, investigators, and all site personnel, as well as Sponsor will be blinded to treatment assignment and to IP (placebo or pegozafermin) throughout the Main study. In the Extension study, specifically-identified Sponsor personnel will not be blinded; however, subjects, investigators and site staff will remain blinded to IP (placebo or pegozafermin). However, the dose regimen (QW or Q2W) will be known to all parties involved in both the Main and the Extension study. Liver biopsies will be read centrally by liver pathologists who are blinded to the treatment group assignment and study visit. Results of the following assessments post Study Day 1, including but not limited to, liver biopsy, MRI, PK and ADA, will be considered as potential unblinding information and will remain blinded throughout the study, unless specified otherwise.

Specifically-identified Sponsor personnel will be unblinded for decision-making purposes and interactions with the FDA after all subjects complete the Week 24 assessments in the Main study. Sponsor personnel responsible for day-to-day study operations will remain blinded, including the Sponsor and CRO Medical Monitors. A formal unblinding plan will be established prior to the unblinding for Week 24.

Other specified personnel or independent vendors may be unblinded based on their study role. These individuals include those who analyze PK or immunogenicity samples in the bioanalytical laboratories, and manage the unblinded data, manage IP inventory, manage expedited reporting of suspected unexpected serious adverse events (SUSARs), and who conduct unblinded analyses for the DMC. DMC members will have access to unblinded data for the purposes of reviewing unblinded overall safety results (Section 9.8).

6.4.4. Unblinding of an Individual Subject

The IRT system will be programmed with blind-breaking instructions. In case of a medical emergency, the Investigator has the sole responsibility for determining if unblinding of a

subject's randomized treatment is warranted. Subject safety must always be the first consideration in making such a determination. If the Investigator decides that unblinding is warranted, the Investigator, when possible, should make efforts to contact the Medical Monitor (or designee) to discuss unblinding a subject's treatment assignment before doing so, unless this could delay emergency medical treatment of the subject. If a subject's treatment assignment is unblinded, the Sponsor must be notified within 24 hours after breaking the blind. The date and reason that the blind was broken must be recorded in the source documentation and IRT.

Appropriate personnel at the Sponsor (or designee) will unblind SUSARs for the purpose of regulatory reporting. The Sponsor (or designee) will submit SUSARs to Regulatory Agencies in blinded or unblinded fashion according to local law. The Sponsor (or designee) will submit SUSARs to Investigators in a blinded fashion.

Appropriate personnel at the Sponsor (or designee) will have access to unblinded individual subject treatment assignments for the purposes of study-required activities including management of IP inventory, production of summary tables and figures for DMC review, and performance of bioanalytical analysis of PK concentrations. These personnel will not be involved in data collection or final analysis of safety and efficacy results. Subjects, investigators, and other site personnel who are directly involved in the conduct of the study, collection of the data, and analysis of the final safety and efficacy results will remain blinded to treatment assignments until after the completion of the study and the database has been locked.

6.5. Investigational Product Compliance

When subjects are dosed at the site, they will receive IP directly from the Investigator or designee, under medical supervision. The date and time of each dose administered in the clinic will be recorded in the source documents and recorded in the eCRF. The dose of IP and study subject identification will be confirmed at the time of dosing by a member of the study site staff other than the person administering the IP.

Details on IP compliance at remote/home visits are provided in the Home Administration Instructions or Pharmacy Manual. The allowed time window for dosing is ± 2 days. If a subject wishes to change their dosing schedule (e.g., to a different day of the week), the Investigator should discuss with the Sponsor.

6.5.1. Guidance for Missed Dose(s)

The IP dosing window is ± 2 days however for QW dosing, every effort should be made to take IP on the same day of the week and must be at least 5 days between 2 doses. If more than 3 days (72 hours) have elapsed from the scheduled dosing for either QW or Q2W, subjects will be instructed to skip the missed dose. The Medical Monitor (or designee) should be contacted if there are any questions on missed doses.

6.6. Treatment of Overdose

There is no experience with overdose of pegozafermin in humans. In Study TV47948-SAD-10122, single doses of pegozafermin at doses up to 78 mg were safe and well tolerated in healthy subjects.

For this study, any dose of IP greater than the highest protocol-specified dose will be considered an overdose.

The Sponsor does not recommend specific treatment for an overdose.

In the event of an overdose, the Investigator should be notified by the subject and:

- Contact the Medical Monitor (or designee) immediately.
- Closely monitor the subject for any AEs and laboratory abnormalities for at least 30 days.
- Obtain a serum sample for PK analysis within 2 days from the date of the overdose if requested by the Medical Monitor (or designee) (determined on a case-by-case basis).
- Document the quantity of the excess dose as well as the occurrence of the overdose in the eCRF.

6.7. Concomitant Therapy

Any medication (including over-the-counter or prescription medicines, vitamins, and herbal supplements) or vaccine that the subject is receiving at the time of enrollment or receives during the study must be recorded along with at least the following information:

- Reason for use
- Dates of administration including start and end dates
- Dosage information including dose and frequency and route of administration

It has previously been reported that NAFLD is associated with reduced CYP3A drug metabolism activity *in vivo* and hepatic CYP3A4 expression in humans ([Woolsey, 2015](#)). In addition, based on the work by Woolsey et al it is suggested that exogenously administered FGF21 may decrease hepatic CYP3A4 activity ([Woolsey, 2016](#)). The underlying mechanism has not been fully elucidated.

Subjects receiving concomitant administration of CYP3A4 substrates with narrow therapeutic index should be closely monitored for any potentially related safety events, and dose adjustment of the CYP3A4 substrate should be considered as needed.

Short-term use of sliding scale insulin therapy during a medical procedure or hospitalization (<5 days) for subjects with T2DM may be performed as needed.

The Medical Monitor (or designee) should be contacted if there are any questions regarding concomitant or prior therapy.

6.7.1. Prohibited Medications/Therapies

Prohibited therapies include:

- Bariatric surgery
- Elective bone surgery for any bone disorders
- Medications historically associated with secondary NAFLD requiring >2 weeks of pharmacologic dosing . These include amiodarone, methotrexate, glucocorticoids,

tetracyclines, tamoxifen, estrogens or anabolic steroids at doses greater than those used for hormone replacement.

- Other hepatotoxic agents including but not limited to, nefazodone, isoniazid, valproate, and carbamazepine.
- The TNF (tumor necrosis factor) antagonists, adalimumab, etanercept and certolizumab, infliximab or sulfasalazine are prohibited during the Main Study but may be considered for managing emerging AEs in the Extension Study.
 - Short-term oral steroid bursts with/without taper as well as topical and inhaled corticosteroids are allowed.
- Antidiabetic medications: Thiazolidinediones (e.g., pioglitazone) are prohibited throughout study to minimize risk of confounding effect with pegozafermin treatment. Dose adjustments or switching from one medication to another within the same drug class are allowed after randomization for DPP-IV inhibitors (“gliptins”), SGLT2 inhibitors (“gliflozins”) and GLP-1 agonists (“glutides”, including semaglutide [Ozempic]); However, initiation of new DPP-IV inhibitors, SGLT2 inhibitors, or GLP-1 agonists is not allowed during screening and the Main Study (e.g., switching from a DPP-IV inhibitor to a GLP-1 agonist is not allowed, but switching from one DPP-IV inhibitor to another DPP-IV inhibitor is allowed). Initiation of these agents for uncontrolled hyperglycemia (but not for weight loss) may be allowed during the Extension Study with the Medical Monitor’s approval.
- Vitamin E (> 400 IU/day) should not be initiated, or dose increased during the study.
- Any investigational product, FGF21 analogs (e.g., LY2405319, LY3025876, BMS-986036, BMS-986171, PF-05231023, AKR-001, pegozafermin), or FGFR1-activating products. Note: study participants will not be allowed to participate in other interventional trials for FGF21 analog or FGFR1 activating products, during the immunogenicity follow up period.
- Weight loss medications (including GLP-1 agonists specifically for weight loss) should not be initiated during the study.

The Investigator should discuss any questions regarding allowed/prohibited medications with the Medical Monitor (or designee). The final decision on any supportive therapy rests with the Investigator. However, the decision to continue the subject on IP requires the mutual agreement of the Investigator and the Sponsor.

6.8. Intervention after the End of Study

No additional intervention is planned beyond the end of the study.

7. DISCONTINUATION OF IP AND SUBJECT DISCONTINUATION/WITHDRAWAL

7.1. Discontinuation of Investigational Product and Subject Withdrawal from the Study

In some instances, it may be necessary for a subject to permanently discontinue IP. Temporary IP interruption may be allowed if Investigator and Medical Monitor (or designee) assess that IP rechallenge is safe and appropriate.

Permanent discontinuation of IP at any time during the study does not mean withdrawal from the study, and the subject will be encouraged to remain in the study, complete the Early Termination (ET) visit at the time of IP discontinuation and continue to complete remaining study period during the Main Study or the Extension Study as appropriate (i.e., subjects who ET before Week 24 may complete study visits through Week 24 and subjects who ET after Week 24 may complete visits through Week 48). Procedures for the remaining visits will include assessment of AEs and updating concomitant medications. Subjects who permanently discontinue IP at or after Week 16 and before Week 24 of the Main study will be requested to provide a liver biopsy at ET visit. (Section 1.3).

Subjects who experience clinically significant TEAEs that are assessed as a potential risk to subject safety will be discontinued from IP and undergo an ET visit as specified in the SoA. The decision to discontinue IP will be made by the Investigator and should be discussed with the Medical Monitor (or designee). If any subject experiences a Grade 3 TEAE that is considered related to IP, the Investigator should discuss treatment discontinuation with the Medical Monitor (or designee).

Subjects have the right to withdraw from the study at any time and for any reason without prejudice to their future medical care by the Investigator or at the institution. The reason for subject withdrawal from the study will be recorded in the eCRF. At the time of withdrawal from the study, the ET visit should be conducted as shown in the SoA.

A subject may discontinue IP or withdraw from the study for the following reasons:

- Adverse event
- Death
- Lack of efficacy
- Lost to follow-up
- Non-compliance with study drug
- Physician decision
- Pregnancy
- Protocol deviation
- Site terminated by Sponsor
- Study terminated by Sponsor

- Withdrawal by subject
- Randomized by mistake
- Evidence of hepatic decompensation including ascites, hepatic encephalopathy, splenomegaly, or variceal bleeding as assessed by the Investigator (for F4 subjects only).
- MELD Na⁺ score >12 (for F4 subjects only)

For liver chemistry abnormality actions and follow-up assessments, refer to Section [7.1.1](#).

Pregnancy is a mandatory criterion for permanent discontinuation of IP (Section [7.1.2](#)).

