7.8. Efficacy Analysis for Main Study

The primary efficacy endpoints are (1) proportion of subjects with NASH resolution without worsening of fibrosis at Week 24 compared to baseline (2) proportion of subjects achieving improvement of fibrosis ≥ 1 stage without worsening of NASH at Week 24 compared to baseline. The following hypothesis will be tested for each primary endpoint:

- The null hypothesis: there is no difference in the proportion of subjects meeting the primary endpoint between the placebo and each pegozafermin dose group.
- The alternative hypothesis: the proportion of subjects meeting the primary endpoint between the placebo and each pegozafermin dose group is different.

The study will be considered successful if a given pegozafermin dose group is demonstrated to be superior to the placebo group in either of the two primary endpoints at 0.05 significance level.

Estimand Framework

As detailed in the ICH E9 (R1) addendum, the following five attributes will define the estimand framework in this trial. The primary estimand will be defined as a treatment policy (TP) estimand, which compares treatment outcomes in two randomized arms at 24 weeks post-randomization irrespective of what changes in treatment could have occurred post-randomization as a result of various intercurrent events (ICE). To implement TP strategy, it will be important that outcomes are collected and recorded after occurrence of ICE's as close to the 24 week time point, regardless of what actual treatment the patient may be receiving. Below are the 5 attributes of the primary estimand:

- Treatment conditions: Randomization to Pegozafermin (15 mg QW or 30 mg QW or 44 mg Q2W) or Placebo, regardless of ICE's and deviations from the randomized treatment and actual treatment received during or at the end of the treatment period.
- Population: Randomized subjects with fibrosis stage 2 or 3 and NAS ≥ 4 at baseline per 3-panel consensus read who received at least 1 dose of IP.
- Endpoints: NASH resolution without worsening of fibrosis at Week 24 compared to baseline; improvement of fibrosis ≥ 1 stage without worsening of NASH at Week 24 compared to baseline
- Intercurrent events (ICEs): Three types of ICEs are defined below.
- Population-level summary: Between treatment group difference expressed in terms of the percentage differences in achieving the endpoints.

The following types of ICEs will be documented in course of the study.

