- ICE-1: Discontinuation of treatment due to lack of efficacy.
- ICE-2: Discontinuation of treatment due to adverse events (AE).
- ICE-3: All other events, i.e., protocol deviation, etc.

The primary analysis will use all observed outcomes at Week 24, regardless of actual treatment. All outcomes collected from patients experiencing this ICE after the actual ICE will be used in the analysis and missing values resulting from any ICE will be imputed assuming an imputation model informed by observed outcomes from similar patients with this type of ICE. The imputation model will include terms for the randomized treatment arm and the type of ICE(s) experienced by patients with missing outcomes, i.e., ICE-1,2,3 (as defined above) or None. The final inference following multiple imputation (MI) will be conducted using Rubin's combination rules.

Although the ICEs' defined above will be all handled by the same treatment policy strategy for the primary estimand, various sensitivity analyses (SA) will be conducted that will incorporate different strategies, depending on the type of ICE. For the purposes of sensitivity analysis, patients who experienced any of the listed ICEs (ICE-1,2,3), the outcomes for the primary efficacy endpoint will be considered missing starting from the occurrence of each ICE (even if outcomes are collected following an ICE) and then the missing outcomes will be imputed using appropriate imputation strategies.

For ICE-1, the SA will use the "return to baseline" hypothetical strategy, implying no benefits have been received for such patients from randomization until the end of the treatment period. The missing outcomes will be imputed using a relevant regression model fitted to the baseline data within each treatment arm with patient age, gender, baseline NAS score and stratification factors included as covariates.

For ICE-2, SA will be handled with the "control-based" hypothetical strategy implying that patients would have switched to the control treatment (i.e., placebo) starting from the occurrence of ICE-2 to the end of the treatment period. The missing outcomes will be imputed from a similar regression model fitted to the placebo arm alone with patient age, gender, baseline NAS score and stratification factors as covariates.

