For ICE-3, SA will be handled using a hypothetical strategy that assumes that patients would have continued their assigned treatment starting from ICE-3. The missing outcomes will be imputed using the same model as for ICE-2 but fitted to each respective treatment arm.

Missing data due to reasons unrelated to the intercurrent events (ICE-1, 2, 3), e.g., missingness caused by study termination by sponsor, will be imputed using the same model as for ICE-3.

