7.8.1.1. Primary analysis

The primary analysis will be carried out using an MI-based strategy that includes the following three steps:

- Step 1. Missing outcomes will be imputed a large number of times ($M=100$) using PROC MI based on the model outlined in Table 5 based on a logistic regression model.
- Step 2. The Cochran-Mantel-Haenszel (CMH) test stratified by T2DM status (yes vs. no) and fibrosis stage (F2 vs. F3) will be applied to each completed data set to compare the proportions of responders at Week 24 between each pegozafermin group and placebo, adjusting for the stratification factors. The point estimates and associated standard errors for the differences in proportions as well as CMH test statistics will be calculated.
- Step 3. The CMH summaries from individual completed sets will be combined using Rubin’s rules to produce a single inferential statement (treatment effect, standard error, 95% confidence interval and p-value) via PROC MIANALYZE.

Note that a patient can have only one ICE (classified as ICE-1, -2, -3) or none (0). Once an ICE of specific type has occurred, the status of ICE variables remains fixed at that value until the end of the trial. All collected data are used in imputation. Imputation is done by the trial arm (TRT) but, if the data are sparse, instead of imputing by TRT, include TRT as covariate.

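### Death is not named in the estimand, so a subject who dies without a usable biopsy is imputed in the primary analysis and can count as a responder

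*Protocol*

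**What the plan says.** Protocol 7.1 has a list headed "A subject may discontinue IP or withdraw from the study for the following reasons". Death and adverse event are separate items on it.

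SAP 7.8 (and Protocol 9.1.1 in matching terms) defines the estimand: "The primary estimand will be defined as a treatment policy (TP) estimand". It recognises three intercurrent events: stopping treatment for lack of efficacy (ICE-1), stopping for adverse events (ICE-2), and a catch-all, "ICE-3: All other events, i.e., protocol deviation, etc". None of them names death.

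For the primary analysis, "missing values resulting from any ICE will be imputed assuming an imputation model informed by observed outcomes from similar patients with this type of ICE". SAP 7.8.1.1 carries this out: "Missing outcomes will be imputed a large number of times" (M=100), by logistic regression within arm, or with arm as a covariate if data are sparse. Table 5 adds ICE type as a covariate but drops it if most subjects with an ICE lack outcomes.

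In the per-ICE sensitivity analysis, ICE-2 subjects are imputed from placebo. For ICE-3 the analysis "assumes that patients would have continued their assigned treatment starting from ICE-3". Missing data unrelated to any ICE use the ICE-3 model.

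The Full Analysis Set (SAP 6) requires at least one dose and does not remove a subject who later dies.

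**The concern.** A treatment-policy estimand asks what the biopsy shows at Week 24 whatever happened to treatment. That question has an answer for a subject who stopped the drug and none for a subject who has died. Imputation supplies a value that could never have been observed, and the value can be a response. Continuing assigned treatment is no better as a scenario for a dead subject.

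The direction also matters. At the planned rates an imputed death earns more credit on pegozafermin than on placebo, so the distortion favours the drug even if deaths are balanced between arms of equal size. If a death occurs and no rule exists, the sponsor must either report a dead subject as a partial responder or change the rule after the fact.

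**Working it through.** **Following one subject through the plan.** Take a dosed Full Analysis Set subject who dies before Week 24 with no post-baseline biopsy.

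| Analysis | If classed ICE-3, or not an ICE | If classed ICE-2 |
|---|---|---|
| Primary (7.8.1.1) | imputed, can respond | imputed, can respond |
| Per-ICE sensitivity (7.8.1.2.1) | imputed as if assigned treatment continued | imputed from placebo |
| Missing = non-responder (7.8.1.2.4) | non-responder | non-responder |
| Completer (7.8.1) | omitted | omitted |

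For the key secondary endpoints, SAP 7.8.2 repeats only the primary and completer analyses. There the subject is either imputed or omitted, and never counted as a non-responder.

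**Inputs (SAP 3.5).** Planned response is 15% and 20% on placebo and 45% and 50% on pegozafermin, for NASH resolution and fibrosis improvement respectively. Planned N is 64 for pooled placebo, 64 for 30 mg QW, 40 for 44 mg Q2W and 16 for 15 mg QW. Dropout is up to 15%, alpha 0.05 two-sided.

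**The plan's own power first.** Evaluable n is 0.85 × 64 ≈ 54 and 0.85 × 40 = 34. The pooled-variance normal approximation is

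power = Φ{[(p2 − p1) − 1.96·√(p̄(1−p̄)(1/n1+1/n2))] / √(p1(1−p1)/n1 + p2(1−p2)/n2)}.

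For 30 mg QW and NASH resolution, p̄ = 0.30, so power = Φ[(0.30 − 1.96 × 0.0882)/0.0833] = Φ(1.53) = 93.7%. Fibrosis improvement gives 91.6%. For 44 mg Q2W the results are 87.0% and 83.9%. The SAP states 94%, 92%, 87% and 83%, so its figures reproduce and are not in dispute.

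**Shift per death.** Neither document gives a death rate, so 1 or 2 deaths in an arm is an assumption. Suppose each death is imputed at its arm's planned rate p. Compared with counting it as non-response, the arm's expected rate rises by p/N:

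- 30 mg QW: 0.45/64 = 0.70 and 0.50/64 = 0.78 points; two deaths, 1.41 and 1.56.
- 44 mg Q2W: 0.45/40 = 1.125 and 0.50/40 = 1.25 points; two deaths, 2.25 and 2.50.
- 15 mg QW, at the same rates: 0.45/16 = 2.8 and 0.50/16 = 3.1 points.
- Placebo: 0.15/64 = 0.23 and 0.20/64 = 0.31 points.

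One death in each of 30 mg QW and placebo widens the difference by (0.45 − 0.15)/64 = 0.47 points. The fibrosis endpoint gives the same figure.

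If a death is classed ICE-2, the per-ICE sensitivity analysis uses placebo rates: 0.23 to 0.31 points at N=64, and 0.15/40 = 0.38 to 0.20/40 = 0.50 points at N=40.

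**Power under a non-responder rule.** As a rough guide, the active rate is lowered by p/N per death, with deaths in the active arm only and evaluable n as above:

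| Comparison with placebo | 0 deaths | 1 death | 2 deaths |
|---|---|---|---|
| 30 mg QW | 93.7% / 91.6% | 92.7% / 90.2% | 91.5% / 88.7% |
| 44 mg Q2W | 87.0% / 83.9% | 84.7% / 80.9% | 82.1% / 77.7% |

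Each cell gives NASH resolution, then fibrosis improvement.

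**The case against.** **Classification.** A reader might infer from the separate entry in Protocol 7.1 that every death is ICE-3. The documents do not say so. No section maps disposition reasons to ICE types. Protocol 10.3 treats an AE-related death as the highest AE grade, and SAP 7.10.1 lists fatal AEs, so a fatal AE could be ICE-2. That stands. It limits the continued-treatment criticism to one possible coding, but it does not rescue the primary analysis, which imputes after any ICE.

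**Existing safeguards.** It is tempting to say that only the missing-as-non-responder analysis avoids the problem. The completer analysis also avoids crediting a death, because it leaves the subject out. Both are secondary to the primary analysis, and only the completer analysis carries over to the key secondary endpoints and the subgroups.

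**Size.** The points per death might be read as expected averages. They assume the full planned arm rate. The primary model may carry an ICE-type term and borrow from subjects with the same kind of event, who need not respond at that rate. The figures are therefore conditional on that assumption.

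**What is imputed.** Binary responder status is drawn; no biopsy scores are created.

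**Materiality.** Protocol 2.3.1 reports no deaths in the earlier Phase 1b/2a study. With none here, nothing changes. The list in Protocol 7.1 is also an ordinary set of disposition reasons with no error in it; the gap lies in the estimand.

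**Conclusion.** The point holds as a minor gap. No section exempts death, so the rules as written allow a subject who has died to be counted as a histological responder in the primary analysis, and in the per-ICE sensitivity analysis under any classification. For the key secondary endpoints no stated analysis counts such a subject as a non-responder.

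Under the planned-rate assumption, two deaths move the 30 mg QW rate by at most about 1.6 points and the 44 mg Q2W rate by 2.5, against a planned difference of 30 points. A reader might go further and infer that a positive result could rest on imputed deaths. The documents do not support that: they give no death rate, and shifts of this size matter only near the significance boundary. The reason to act is that the estimand is undefined for these subjects and the rule should be set before any death has to be adjudicated.

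**What to change.** In SAP 7.8, Table 5 and 7.8.1.1, name death as its own intercurrent event, separate from ICE-1 to ICE-3, and handle it by a composite strategy. Suggested rule:

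> A subject who dies without an evaluable post-baseline biopsy that qualifies for the Week 24 analysis is a non-responder for the primary and key secondary responder endpoints, in the primary analysis and in all imputation-based sensitivity analyses. A biopsy collected before death is used as observed.

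The last sentence is needed. Protocol 7.1 requests an early-termination biopsy from subjects who stop treatment from Week 16 onwards, and the SAP 6.2 window for Week-24-only parameters opens at day 2, so such a biopsy can be the Week 24 outcome. A rule covering every death before the Week 24 visit would discard collected data, contrary to Table 5.

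An SAP edit is enough, because Protocol Section 9 gives the SAP precedence. A protocol amendment would need ethics approval (Protocol 10.1.1), so Protocol 9.1.1 can be aligned if it is next amended. The edit should be made before unblinding for the primary analysis. The cost is a few sentences, an explicit change of strategy for this one event, and a marginally less favourable rate in any arm with a death.
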